13.6.1 Efficacy Analysis

The change from baseline to Week 12 in PANSS-T, PANSS-P, PANSS-N, and PANSS-G scores will be summarized separately by treatment arm for each visit. Associated baseline scores will be taken as the last corresponding measurement prior to the first dose of IMP in the treatment period (e.g., Visit 3).

The change from baseline in each score will be analyzed separately using a mixed-effects repeated measures (MMRM) model. The corresponding model will include stratification factors, associated baseline, visit, treatment arm, visit by treatment arm interaction and visit by associated baseline interaction as fixed effects, and visit repeated within each participant as a repeated effect. An unstructured covariance matrix will be used to estimate the variance-covariance structure within

EudraCT Number: 2019-003369-16 Clinical Protocol Global V3, 23Mar2021

participants across time points. If convergence is not obtained, then other covariance structures to be used will be specified in the SAP. Objective criteria for assessing normality assumptions and proposed alternative analyses will be specified in the SAP.

[figure not shown]
From this analysis the least squares (LS) mean estimates for each treatment arm at each visit, along with the standard error and 95% confidence intervals (CIs) will be presented separately for each endpoint. In addition, estimates of the treatment difference at each visit will be presented along with standard errors of the difference and 95% CIs. The primary comparison for each endpoint is the estimate of the treatment difference at Week 12.

For participants who complete the trial, regardless of whether IMP is discontinued or not, the visit effect used in the analysis will correspond to the associated score at each trial visit (e.g., Visits 4, 5, 6, and 7). However, participants who withdraw from the trial are required to complete the procedures at Visit 7 at the time of withdrawal. For these participants, Visit 7 data will be assigned to the nearest post-baseline visit (for which the assessment is scheduled to be performed), based on the trial day of the visit. Further details will be specified in the SAP.

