5.5.2.1 PANSS-T

The SCI-PANSS is a medical scale used for measuring symptom severity of participants with schizophrenia or related psychotic disorder. The name refers to the 2 types of symptoms in schizophrenia, as defined by the American Psychiatric Association: positive symptoms, which refer to an excess or distortion of normal functions (e.g., hallucinations and delusions), and negative symptoms, which represent a diminution or loss of normal functions.

It is a 30-item rating instrument that assesses the positive and negative symptoms of schizophrenia as well as symptoms of general psychopathology. Individual items are rated on a 7-point scale, where 1 = absent and 7 = extreme. A PANSS-T score is derived from the sum of the 30 items and the total score ranges from 30 to 210. Missing data will be handled as specified in Section [5.1.1.1](#). This scale will be measured at each assessment visit, with the primary time point of interest being Day 85.

The change from baseline in PANSS-T score will be analyzed using a mixed-effects repeated measures (MMRM) model. An MMRM model will be fitted to the change in PANSS-T score at each visit and will include stratification factors (sex [male or female] and region [North America or Europe]), associated baseline, visit, treatment arm, visit by treatment arm interaction and visit by associated baseline interaction as fixed effects and

visit repeated within each participant as a repeated effect. For the analysis of the PANSS-T score; baseline PANSS-P, baseline PANSS-N and PANSS-G will be included in the model as fixed effects for the associated baseline instead of baseline PANSS-T.

The PROC MIXED procedure in SAS will be utilized to perform the analysis. An unstructured covariance matrix will be used to estimate the variance-covariance structure within participants across time points. If convergence is not obtained, or model fit is not adequate then other covariance structures will be explored in the following order until the model converges:

- Toeplitz
- First-order autoregressive
- Compound Symmetry

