This order is specified according to a decreasing number of covariance parameters in the structure. The primary analysis will use the first covariance structure converging to the best fit. If a structured covariance is used, the sandwich estimator for the covariance estimation will be used by specifying the EMPIRICAL options in the PROC MIXED procedure in SAS with the aim to deal with model misspecification of the covariance matrix.

The least squares (LS) mean estimates for each treatment arm at each visit, along with the standard error and 95% confidence intervals (CIs) will be presented. In addition, the estimate of the treatment difference at each visit will be presented along with standard errors of the difference and associated 95% CIs. The primary comparison is the estimate of the difference at Day 85.

For participants who complete the trial, regardless of whether IMP is prematurely discontinued or not, the visit effect used in the analysis will correspond to the associated score at each trial visit. However, participants who withdraw from the trial are required to complete the procedures for End of Treatment at the time of withdrawal. For these participants, their End of Treatment data will be assigned to the nearest post-baseline visit (for which the assessment is scheduled to be performed), based on the trial day of the visit.

The values including change from baseline for PANSS-T will be summarized using standard summary statistics for the full analysis set.

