5.5.2.5 CGI-S

The CGI-S is a 7-point scale used to rate the severity of participants' illness at the time of assessment. Considering total clinical experience, a participant will be assessed on severity of mental illness at the time of rating 0 = not assessed; 1 = normal, not at all ill; 2 = borderline mentally ill; 3 = mildly ill; 4 = moderately ill; 5 = markedly ill; 6 = severely ill; or 7 = among the most extremely ill participants. The CGI-S will be assessed at Visits 1, 2, 3, 4, 5, 6 and 7.

The numeric values of CGI-S assessments will be analyzed separately using the same MMRM approach as specified in Section 5.5.2.1. Baseline CGI-S score will be included as a covariate. Both values for the original categorical scale and the converted numerical scale at each visit including change from baseline for the CGI-S numerical scale will be summarized using standard summary statistics for the full analysis set.

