5.5.2.6 CGI-I

The CGI-I is a 7-point scale that requires the clinician to assess how much the participant's illness has improved or worsened relative to a baseline state at the beginning of the intervention. This is rated as: 0 = not assessed; 1 = very much improved; 2 = much improved; 3 = minimally improved; 4 = no change; 5 = minimally worse; 6 = much worse; or 7 = very much worse. The CGI-I will be measured at Visits 4, 5, 6 and 7.

[figure not shown]
The numeric values of CGI-I assessments will be analyzed separately using the same MMRM approach as specified in Section 5.5.2.1. Baseline CGI-S will be included as a covariate. Both values for the original categorical scale and the converted numerical scale at each visit will be summarized using standard summary statistics for the full analysis set.

A series of five horizontal black bars of increasing length, followed by a small black square.

[REDACTED]

[REDACTED]

[REDACTED]

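### An undefined model-fit judgment can displace a converged unstructured MMRM, and the fallback's uncorrected sandwich 95% CI covers only about 92% to 94% at n = 80

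*SAP*

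**What the plan says.** Protocol 13.6.1 specifies an unstructured covariance and one reason to leave it: "If convergence is not obtained, then other covariance structures to be used will be specified in the SAP". The sentence after that concerns a different check, normality, and promises that "Objective criteria for assessing normality assumptions and proposed alternative analyses will be specified in the SAP".

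SAP 5.5.2.1 keeps unstructured (UN) as first choice but allows two routes out: non-convergence, "or model fit is not adequate then other covariance structures will be explored in the following order until the model converges". The order is Toeplitz, first-order autoregressive (AR(1)), compound symmetry (CS). It then adds: "The primary analysis will use the first covariance structure converging to the best fit". No fit statistic, threshold or decision-maker is named.

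On standard errors: "If a structured covariance is used, the sandwich estimator for the covariance estimation will be used by specifying the EMPIRICAL options". The software is fixed too: "The PROC MIXED procedure in SAS will be utilized to perform the analysis". Neither document names a denominator degrees-of-freedom (df) method or a small-sample correction.

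The three subscales (SAP 5.5.2.2 to 5.5.2.4) follow the same approach. CGI-S is "analyzed separately using the same MMRM approach as specified in Section 5.5.2.1", and for CGI-I, "The numeric values of CGI-I assessments will be analyzed separately using the same MMRM approach".

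SAP 3.2 records that 80 participants were randomized before early termination. SAP 5.5.1 plans no formal test and presents point estimates and 95% CIs, with p-values only as flags.

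**The concern.** There are two linked problems.

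**The route into the fallback is undefined.** A UN model that has converged can be dropped on an unstated view of its fit. The selection rule also pulls two ways: stepping down a list until something converges is a convergence rule, while choosing by best fit is a comparison. They can pick different models, and different models for different endpoints.

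**The fallback's intervals are too narrow at this sample size.** The classical sandwich protects against a wrong covariance structure, which is the SAP's stated aim, and it largely does so here. But it is biased downward with few independent units, and there are about 27 participants per pooled arm, fewer at Day 85.

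With hypothesis testing set aside, the validity of the 95% CI is what the efficacy analysis has left. In every simulated setting the standard-error bias ran toward overstated precision.

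**Working it through.** **The plan's own figure.** Inputs from SAP 3.2: SD 11.0, difference 4.32, two-sided 0.05, 80% power, 15% drop-out. Per arm, n = 2 × (1.960 + 0.842)² × 11² / 4.32² = 101.8, so 102. A t test with 103 per arm (309 in total) has 80.1% power. 309 / 0.85 = 363.5, so 364, against 366 stated. The planned figure reproduces. The documents state no coverage figure for the fallback, so that was simulated at the size actually reached.

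**Size and model.** 80 / 3 gives arms of 26, 27 and 27. At Day 85, 15% missing leaves 80 × 0.85 = 68; 35% missing leaves 52. The PANSS-T model has 26 fixed effects: intercept 1, sex 1, region 1, visit 3, treatment 2, visit by treatment 6, and three baselines each by four visits 12. One-baseline models have 14 + 4 = 18.

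**When could fit displace a converged UN?** Toeplitz, AR(1) and CS are special cases of UN, so none can have a higher likelihood. Only a parsimony penalty can prefer them. Parameters: UN 4 × 5 / 2 = 10, Toeplitz 4, AR(1) 2, CS 2. UN survives against Toeplitz only if it lowers −2 log-likelihood by more than 2 × 6 = 12 (AIC) or ln(80) × 6 = 26.3 (BIC). The choice of criterion therefore matters. Displacement of a converged UN in simulation:

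| | AIC | BIC |
|---|---|---|
| PANSS-T, SD rising over visits | 0% to 1.5% | 10% to 43% |
| PANSS-T, constant SD | 51% to 65% | 99% |
| CGI-S and CGI-I | 10% to 28% | 77% to 94% |

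**Coverage simulation.** REML MMRM, 4,000 data sets per setting, two Day 85 contrasts each, no treatment effect, monotone random loss. Assumed, because the documents do not give them: correlation 0.6 or 0.8 per 4 weeks; SD 7/8/9.5/11 or 11 throughout; 15% or 35% missing at Day 85 (SD 11 and 15% come from SAP 3.2). That makes 8 PANSS-T settings. Six further settings cover the subscale, CGI-S and CGI-I models (correlation 0.8, rising SD; CGI scores as rounded latent normals). The Monte Carlo SE of coverage is at most √(0.08 × 0.92 / 4000) = 0.4 points.

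| Coverage of nominal 95% CI | PANSS-T | Subscale and CGI |
|---|---|---|
| UN, model-based SE, between-subject df | 94.3% to 95.2% | 94.5% to 95.3% |
| UN, model-based SE, within-subject df | 94.1% to 95.0% | not separated |
| UN, Kenward-Roger | 94.6% to 95.3% | not separated |
| Toeplitz, AR(1) or CS with EMPIRICAL | 91.9% to 93.6% | 92.8% to 94.3% |
| Paired loss against UN (between-subject df) | 1.3 to 2.5 points | 0.9 to 1.8 points |

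EMPIRICAL SEs for PANSS-T were 5% to 9% too small. A hand check agrees: an SE 5% too small turns 1.96 into 1.86 (93.7% coverage), and 9% too small turns it into 1.78 (92.6%). Variability of the sandwich itself takes a little more.

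**Widths.** Mean half-width was 6.1 to 7.0 points for Toeplitz with EMPIRICAL and 6.5 to 7.4 for UN. By hand for UN: 1.994 × 11 × √(2 / 22.7) = 6.5 with 68 completers, and 1.994 × 11 × √(2 / 17.3) = 7.5 with 52. The Day 85 estimate differed across the four structures by a median of 0.3 to 0.8 points (90th percentile 0.7 to 1.7).

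**Separate checks.** A second simulation, coded independently, gave EMPIRICAL 92.7% to 93.7% against UN 94.7% to 95.0%, a loss of 1.0 to 2.3 points. In it UN combined with EMPIRICAL also covered only 93.0% to 93.8%, so the uncorrected sandwich causes the loss, not the structure. A third gave 91.6% to 94.0% against 93.7% to 95.6%.

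**The case against.** The coverage loss is conditional on entering the fallback. UN converged in all 56,000 simulated fits, so the trigger that both documents share never fired. Applying the whole rule to PANSS-T gives 93.2% to 95.2% if fit is judged by AIC and 92.5% to 94.9% if by BIC, which is milder than the conditional figures. This stands.

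The SAP mentions neither AIC nor BIC, and the displacement rates depend on the assumed truth: the second simulation found 96% under AIC with constant variance, against 51% to 65% in the first. A further check gave 53% to 59% when correlation decayed with time over the unequally spaced visits and 96% to 97% under exact CS, so the gap reflects the assumptions. It also shows that an unnamed criterion leaves the reported model open.

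The clause might be meant only for numerical failure, and the best-fit wording for an optimiser reaching its solution. Both readings are possible, but the text does not say so. Since a restricted structure cannot fit better than UN, deleting the clause loses nothing.

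The protocol's call for objective criteria concerns normality, and it does delegate detail to the SAP. That is correct; the comparison only shows that a judgment-based trigger is out of keeping with it.

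The practical effect is small. No formal test is planned, and half-widths exceed 4.32 points either way. Nor is every fallback interval narrower: for PANSS-T, Toeplitz with EMPIRICAL was narrower than UN in 79% to 85% of contrasts. This stands and limits the weight of the point.

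**Conclusion.** The concern holds. The SAP widens the protocol's trigger without a criterion, states a selection rule that can be read two ways, and attaches to the fallback an interval that falls short of its nominal level at n = 80. Conditional on the fallback, coverage is about 92% to 94%, roughly 1 to 2.5 points below UN.

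The size rests on assumed correlations, SD patterns, random loss and CGI distributions. The number with Day 85 data after early termination is not stated, and the fits were not run in PROC MIXED, whose convergence could differ. The direction and approximate size agreed across the separate simulations. How often the fallback would be used cannot be determined from the documents. The plan should be changed, because the flaw lies in the main efficacy analysis and the repair is cheap, but no conclusion has been shown to turn on it.

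**What to change.** Before unblinding, amend SAP 5.5.2.1 in two parts.

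1. Remove the inadequate-fit trigger and the best-fit wording. For all six endpoints, state that UN is used whenever it converges, and otherwise the first of Toeplitz, AR(1) and CS, in that order, that converges. Name the df method, for example Kenward-Roger for UN. The cost is two deletions and one added phrase.

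2. For the case where UN does not converge, replace the classical sandwich with a small-sample-corrected one (Mancl-DeRouen type, for example PROC GLIMMIX with EMPIRICAL=FIRORES) and between-subject df. It covered 95.2% to 96.2% across all 14 settings. The cost is moving that analysis out of PROC MIXED, slightly conservative coverage, and wider intervals: 11% to 15% wider than with EMPIRICAL for PANSS-T (8% to 11% for the subscale and CGI models), and 5% to 10% wider than UN for PANSS-T. This part matters only if the fallback is used.

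Do not simply drop EMPIRICAL and keep the equal-variance structures with model-based SEs: under rising SDs those covered only 86% to 90% for PANSS-T.

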5.5.2.2 PANSS-P

The PANSS 'P' Scale will be calculated as the sum of the items prefixed with an P, 7 items in total, i.e. delusions, conceptual disorganization, hallucinatory behavior, excitement, grandiosity, suspiciousness/persecution and hostility. The primary time point of interest will be Day 85.

The change from baseline in PANSS-P score will be analyzed using the same MMRM approach as specified in Section [5.5.2.1](#). Baseline PANSS-P will be included in the model as a fixed effect for the associated baseline.

The values including change from baseline for PANSS-P will be summarized using standard summary statistics for the full analysis set.

5.5.2.3 PANSS-N

The PANSS 'N' Scale will be calculated as the sum of the items prefixed with an N, 7 items in total, i.e. blunted affect, emotional withdrawal, poor rapport, passive/apathetic social

withdrawal, difficulty in abstract thinking, lack of spontaneity and flow of conversation and stereotyped thinking. The primary time point of interest will be Day 85.

The change from baseline in PANSS-N score will be analyzed using the same MMRM approach as specified in Section 5.5.2.1. Baseline PANSS-N will be included in the model as a fixed effect for the associated baseline.

The values including change from baseline for PANSS-N will be summarized using standard summary statistics for the full analysis set.

5.5.2.4 PANSS-G

The PANSS 'G' Scale will be calculated as the sum of the items prefixed with a G, 16 items in total, i.e. somatic concerns, anxiety, guilt feelings, tension, mannerisms and posturing, depression, motor retardation, uncooperativeness, unusual thought content, disorientation, poor attention, lack of judgment and insight, disturbance of volition, poor impulse control, preoccupation and active social avoidance. The primary time point of interest will be Day 85.

The change from baseline in PANSS-G score will be analyzed using the same MMRM approach as specified in Section 5.5.2.1. Baseline PANSS-G will be included in the model as a fixed effect for the associated baseline.

The values including change from baseline for PANSS-G will be summarized using standard summary statistics for the full analysis set.

5.5.2.5 CGI-S

The CGI-S is a 7-point scale used to rate the severity of participants' illness at the time of assessment. Considering total clinical experience, a participant will be assessed on severity of mental illness at the time of rating 0 = not assessed; 1 = normal, not at all ill; 2 = borderline mentally ill; 3 = mildly ill; 4 = moderately ill; 5 = markedly ill; 6 = severely ill; or 7 = among the most extremely ill participants. The CGI-S will be assessed at Visits 1, 2, 3, 4, 5, 6 and 7.

The numeric values of CGI-S assessments will be analyzed separately using the same MMRM approach as specified in Section 5.5.2.1. Baseline CGI-S score will be included as a covariate. Both values for the original categorical scale and the converted numerical scale at each visit including change from baseline for the CGI-S numerical scale will be summarized using standard summary statistics for the full analysis set.

5.5.2.6 CGI-I

The CGI-I is a 7-point scale that requires the clinician to assess how much the participant's illness has improved or worsened relative to a baseline state at the beginning of the intervention. This is rated as: 0 = not assessed; 1 = very much improved; 2 = much improved; 3 = minimally improved; 4 = no change; 5 = minimally worse; 6 = much worse; or 7 = very much worse. The CGI-I will be measured at Visits 4, 5, 6 and 7.

[figure not shown]
The numeric values of CGI-I assessments will be analyzed separately using the same MMRM approach as specified in Section 5.5.2.1. Baseline CGI-S will be included as a covariate. Both values for the original categorical scale and the converted numerical scale at each visit will be summarized using standard summary statistics for the full analysis set.

A series of five horizontal black bars of increasing length, followed by a small black square.

[REDACTED]

[REDACTED]

[REDACTED]

5.7.2 Adverse Events

All reported AEs will be classified by system organ class (SOC), preferred term and lower level term using Version 24.1 of MedDRA.

Summaries will be presented by treatment group as well as SOC and preferred term.

A treatment period treatment emergent AE (TEAE) is defined as an AE with a start date on or after the first dose of IMP during the treatment period (Day 1), or an AE that was present prior to the first dose of IMP during the treatment period but has increased its intensity during the treatment period.

If an AE has a partial start date and it is unclear from the partial date (or the stop date) whether the AE started prior to or post first dose of IMP then the AE will be considered treatment emergent and if it is unclear which period the event started, it will be assigned to both periods.

An AE will be considered treatment-related if the plausibility relationship to IMP is recorded on the CRF as 'yes'. If the data on plausibility relationship to IMP is missing then the AE will be considered treatment-related.

An AE will be considered leading to permanent discontinuation of IMP if the action taken with IMP is recorded on the CRF as 'trial medication stopped' or the outcome is recorded on the CRF as 'patient died'.

An AE will be considered leading to IMP dose reduction excluding permanent discontinuation if the action taken with IMP is recorded on the CRF as 'dose reduced', 'dose reduced temporarily' or 'trial medication interrupted'.

An AE will be considered leading to temporary IMP dose reduction if the action taken with IMP is recorded on the CRF as 'dose reduced temporarily'.

An AE will be considered leading to permanent IMP dose reduction excluding permanent discontinuation if the action taken with IMP is recorded on the CRF as 'dose reduced'.

An AE will be considered fatal if the outcome is recorded on the CRF as 'patient died'.

For the summary of TEAEs by maximal severity, for each participant, the worst severity recorded by preferred term, SOC and overall will be used for summary purposes. If severity is missing, the worst case (severe) will be assumed.

For summaries by resolution, AEs with an outcome of 'recovered' or 'recovered with sequelae' will be summarized as 'Resolved' and AEs with an outcome of 'continuing', 'patient died' or those with a missing outcome will be summarized as 'Not resolved'.

For the summary of TEAEs by time of first onset of AE, data will be summarized for the treatment period separately under the following categories:

- Weeks 1–2 (Day 1 to 14).
- Weeks 3–4 (Day 15 to 28).
- Weeks 5–8 (Day 29 to 56).
- Weeks 9–12 (Day 57 to 84).
- >12 weeks (> Day 84).

The time to first onset of AE in treatment period will be calculated for TEAEs as:

$$\text{Start date of AE} - \text{Date of first dose of IMP in treatment period} + 1$$

If participants have multiple occurrences of an AE then the AE will be counted once for the first occurrence only. Percentages will be based on the number of participants in the safety analysis set who have a visit or follow-up call within each time period above.

For the summary of TEAEs by time to AE resolution, data will be summarized under the following categories:

- 1 week (≤ 7 days).
- 2 weeks (8–14 days).
- 3 weeks (15–21 days).
- 4 weeks (22–28 days).
- >4 weeks (>28 days).
- Ongoing (for AEs not resolved).

The time to AE resolution will be calculated for TEAEs as:

$$\text{Stop date of AE} - \text{Start date of AE} + 1$$

If participants have multiple occurrences of an AE then the AE will be counted once for the occurrence with the longest time to AE resolution. However, if any of the AEs are not resolved then the AE will be counted once within the 'Ongoing' category.

The start and stop day of the AE relative to the first dose of IMP will be calculated as per Section 5.1.2. For partial dates, if it is clear from the partial date that the start/stop day was prior to the first dose of IMP, then 'pre' will be listed, similarly if it is clear that the event was post the first dose of IMP then 'post' will be listed as the start/stop day as appropriate.

Listings will include the start and stop day of the AE, a flag for treatment emergence, and limited demographic information about the participant (age, sex, race and weight at screening).

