If the severity of an AE fluctuates day-to-day, for example., a headache or constipation, the change in severity should not be recorded each time. Instead, only the worst observed severity should be recorded with AE start and stop dates relating to the overall event duration, regardless of severity.

A severe AE is not the same as an SAE. For example, a participant may have severe vomiting, but the event does not result in any of the SAE criteria above. Therefore, it should not be classed as serious. The severity of an AE will be recorded as 1 of the following:

- Mild: easily tolerated, does not interfere with normal daily activities, does not require intervention.
- Moderate: causes some interference with daily activities; minimal, local or non-invasive intervention indicated.
- Severe: daily activities limited or completely halted; intervention indicated.

E) Causality

Refer to Section 12.5 above.

EudraCT Number: 2019-003369-16 Clinical Protocol Global V3, 23Mar2021

F) Action Taken with Investigational Medicinal Product

This question refers to the action taken with the IMP due to an AE. The action with the IMP must be classed as:

- Dose increased.
- Dose not changed.
- Dose rate reduced.
- Dose reduced.
- Drug interrupted.
- Drug withdrawn.
- Not applicable.
- Unknown.

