13.6.4.2 Adverse Events

Adverse events will be coded according to the Medical Dictionary for Regulatory Activities dictionary.

A treatment-emergent adverse event (TEAE) is one that started, or worsened in severity or seriousness, following the first dose of IMP.

Descriptive presentations of TEAEs will be given by preferred term and SOC for the safety analysis set. The number of participants reporting at least 1 TEAE will be provided. AEs will be summarized in terms of the number of participants with at least 1 event (N) and the percentage of participants with at least 1 event (%).

The following summaries will be produced as a minimum:

- All-causality TEAEs.
- Treatment-related AEs.
- All-causality TEAEs by maximal severity.
- All-causality serious TEAEs.
- Treatment-related serious TEAEs.
- TEAEs reported as leading to permanent cessation of IMP.
- Fatal TEAEs.

Confidential Page 85 of 104

EudraCT Number: 2019-003369-16 Clinical Protocol Global V3, 23Mar2021

In the presentation of safety data, data from the GWP42003-P dose groups will be presented separately and compared with placebo. This will allow the possibility to explore any effects of the dose of IMP on safety endpoints.

Supportive summaries of ADRs will be presented.

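### SAP 5.7.2 drops the protocol's seriousness criterion for treatment emergence, and its onset classes have no place for a worsened event that keeps a start date before Day 1

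*SAP*

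**What the plan says.** Protocol 13.6.4.2 says that a TEAE "is one that started, or worsened in severity or seriousness, following the first dose of IMP".

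SAP 5.7.2 gives two routes to treatment emergence. The first is a start date on or after the first treatment-period dose. The second is an event that "was present prior to the first dose of IMP during the treatment period but has increased its intensity during the treatment period". Seriousness appears in neither.

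The protocol treats severity and seriousness as separate. Section 12.6 states that "A severe AE is not the same as an SAE" and grades severity as mild, moderate or severe. Section 12.2 defines seriousness by consequences such as death, hospitalization, disability or medical significance.

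On onset, SAP 5.7.2 reads "The time to first onset of AE in treatment period will be calculated for TEAEs as" and then gives AE start date minus date of first treatment-period dose plus 1. The results go into five classes. The earliest is Day 1 to 14 and the last is everything after Day 84.

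Protocol 12.5 adds a recording rule: a pre-treatment event that worsens in severity after the first dose of IMP gets a new eCRF record. The rule does not mention seriousness.

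**The concern.** Two documents define the same safety term differently, and the later one is narrower without saying why. Moving the anchor to the treatment period is stated and sensible after a placebo run-in, but it does not require seriousness to be dropped.

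AEs are collected from after screening (Protocol 12.1.1 and 12.6), so some can be ongoing at Day 1. If one of these leads to hospitalization on treatment while its severity grade stays the same, the SAP rule does not make it a TEAE. The severity scale stops at severe, so an event already at that grade cannot increase in intensity at all. The serious-TEAE tables in SAP Appendix 4 are limited to TEAEs, so such an event would not be counted by arm.

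The onset table has a smaller problem. The SAP's second route admits events that were present before Day 1, but the onset classes start at Day 1. A TEAE admitted that way under its old start date appears in the TEAE table and in no onset class, so the two tables need not agree.

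**Working it through.** **1. The two definitions side by side, for an event ongoing at Day 1**

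| What happens in the treatment period | Protocol 13.6.4.2 | SAP 5.7.2 |
|---|---|---|
| Intensity rises, not serious | TEAE | TEAE |
| Becomes serious and intensity rises | TEAE | TEAE |
| Becomes serious, grade unchanged, same record kept | TEAE | Not a TEAE |
| Worsening entered as a new record dated Day 1 or later | TEAE | TEAE, by its start date |

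Only the third row differs. The new-record rule in Protocol 12.5 does not reach it, because that rule is triggered by severity.

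**2. Does this depend on what first dose of IMP means?** The protocol's Definition of Terms counts placebo as IMP, and Appendix 1 places the first IMP dose at Visit 2. The phrase could therefore mean Day 1 or Visit 2.

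- If it means Day 1, the third-row event is a protocol TEAE because it worsened in seriousness.
- If it means Visit 2, an event from the screening period is still a protocol TEAE because it worsened in seriousness. An event that began after the first run-in dose is one by onset alone.

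Under either reading it is a TEAE under the protocol and not under the SAP.

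**3. Onset values.** Formula (SAP 5.7.2): onset = AE start date − date of first treatment-period dose + 1. For a start k days before that dose, onset = −k + 1.

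| Start relative to Day 1 | Onset value | Class |
|---|---|---|
| 42 days before | −41 | none |
| 14 days before | −13 | none |
| 5 days before | −4 | none |
| 1 day before | 0 | none |
| On Day 1 | 1 | Weeks 1–2 |
| 14 days after | 15 | Weeks 3–4 |
| 84 days after | 85 | >12 weeks |

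Every start before Day 1 is unclassified. The class boundaries from Day 1 onward (14/15, 28/29, 56/57, 84/85) leave no gap. The problem is therefore confined to worsened events that keep a pre-Day 1 start date.

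**4. Size of one event.** SAP 3.2 gives 80 randomized and an allocation of 2:2:1:1. Arm counts are not stated, so I assume the ratio held: 80 × 2/6 = 26.7, about 27 per active arm. One event is 1/27 = 3.7 percentage points. With 30 in the arm it is 1/30 = 3.3, and with 24 it is 1/24 = 4.2.

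**The case against.** **The seriousness gap is narrow.** The event must be ongoing at Day 1, become serious on treatment, show no rise in grade and stay on its original record. Protocol 12.6 ties the grades to daily function and need for intervention, so a mild or moderate event that comes to need inpatient care would usually move up a grade and remain a TEAE. Protocol 12.1.1 also counts worsening of a pre-existing condition as an AE, so a site might enter a new one. This stands as to frequency. It does not help an event already graded severe, and it does not explain why the criterion was dropped.

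**The event is not lost.** Listing 16.2.7.4 covers serious adverse events and its title is not limited to TEAEs. SAP 5.7.2 puts a treatment-emergence flag in the listings, and Protocol 12.3 requires all SAEs to be recorded within 24 hours. This stands: a reader might infer that serious events disappear from the report, and the documents do not support that. What is missing is the by-arm count. Any loss from the treatment-related serious tables is narrower still, because Protocol 12.5 treats events that start before the first dose of IMP as unrelated.

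**The new-record rule answers much of the onset point.** A reader might infer that worsened events in general fit no onset class. They do not: an event re-entered under Protocol 12.5 would normally carry an on-treatment start date, meet the SAP's first criterion and have a class. If first dose of IMP in that rule means Day 1, run-in events are covered too; if it means Visit 2, they are not clearly covered. The one-record rule in Protocol 12.6 is weak evidence for a wider gap, because it concerns day-to-day fluctuation. What remains is that the SAP's second criterion itself presupposes records that start before Day 1, and the onset table gives them no place.

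**Time to resolution.** Measuring it from the recorded start is ordinary event duration. Restarting the clock at worsening is a preference, and I do not press it.

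**Conclusion.** The SAP departs from the protocol's TEAE definition without explanation. The departure can remove a serious on-treatment event from the by-arm serious-TEAE tables when the event was ongoing at Day 1, its recorded intensity did not rise and it was not re-entered. This holds whichever dose is meant by the first dose of IMP. Separately, a TEAE that qualifies by worsening and keeps a pre-Day 1 start date has no onset class; events re-entered on worsening are not affected.

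Such events are probably rare. The documents do not show how many exist, or that any does. One would be about 3.7 percentage points of an active arm on the assumption of about 27 participants (3.3 to 4.2 for 30 down to 24).

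It would be tempting to add that serious TEAEs by arm are the trial's main safety comparison. Neither Protocol 13.6.4 nor SAP 3.3.2 ranks the safety endpoints, so that is not supported. The case for acting is simpler: a stated rule conflicts with the protocol on serious events, and correcting it costs almost nothing.

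**What to change.** In SAP 5.7.2:

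- End the second criterion with *or has increased in intensity or become serious during the treatment period*. If the omission was intended, give the reason.
- For worsened events kept as one record, take onset as the date of worsening or of becoming serious where it is recorded. Otherwise add a row to Table 14.3.2.6, *present before Day 1 and worsened*.
- State that the new-record rule in Protocol 12.5 applies at the first treatment-period dose, so that run-in events are handled in the same way as screening-period events.

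The cost is a few lines of SAP text and at most one extra table row. The downside is a slightly higher TEAE count.
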